When attributes of the tinnitus percept change following certain maneuvers or muscle contractions and somatosensory tinnitus is suspected, it suggests an interaction between the somatosensory and auditory systems (Levine, 1999; Shore et al, 2007; Ralli et al, 2017; Marks et al, 2018). Numerous studies have revealed that tinnitus can be somatically modulated in many people (see Ralli et al, 2017 for a review). Tinnitus modulations associated with the somatosensory system and somatic disorders are often attributed to cortical neuroplasticity initiated by subcortical changes occurring at the auditory brainstem level (Shore et al, 2007). The anatomical and physiological connections between the somatosensory and auditory pathways have been well documented (Dehmel et al, 2008; Shore et al, 2007; Shore et al, 2016; Wu et al, 2016) and are shown in Figure 1 (Cherian et al, 2013). The fact that somatic manipulations can directly influence the tinnitus perception for many patients (Shore, 2011) suggests somatosensory tinnitus is an indicator of an underlying musculoskeletal deficit of the head or neck which warrants taking a non-traditional approach to tinnitus management (Sanchez & Rocha, 2011). The Cleveland Clinic, an institution that is at the forefront of providing tinnitus rehabilitative services, has developed a protocol for assessing if tinnitus can be somatically modulated; when it can, the clinic provides these patients with individualized physiotherapy as part of the treatment regimen.

Research Design and Methods

General Summary of Procedures. To accomplish the goals of Aim 1 (address the prevalence of somatosensory tinnitus in Veterans with tinnitus), individuals who are enrolled for care at a VA facility or clinic will be contacted and screened over the phone. Based on the phone screening, a subset of Veterans will be invited to attend one in-person visit. To accomplish the goals of Aim 2 (develop a clinical framework to diagnose, assess, and treat Veterans with somatosensory tinnitus), a subset of Veterans identified with somatosensory tinnitus (knowledge gained at visit 1) will be given the option to attend 3 in-person individualized physiotherapy sessions from the

study physical therapist using an abbreviated therapy protocol modeled after protocols used at the Cleveland Clinic.

Subject Identification/Recruitment

We will use a variety of recruitment methods including any of the following:

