For participants who choose to be consented in-person, after the informed consent and HIPAA authorization forms are reviewed and signed, they will complete a screening evaluation to confirm eligibility for the study. For participants who consented via the IRB-approved Information Sheet, they will be reminded they provided consent over the phone and be asked if they want anything about the nature of the study to be reviewed with them prior to starting the screening procedures. The HIPAA authorization will then be reviewed and signed prior to any study procedures being conducted. In some cases, procedures will be repeated on later visits. Baseline testing includes tinnitus loudness-matching using an audiometer (optional) and a musculoskeletal screening exam. The following questionnaires will also be administered: Tinnitus Screener, Health History Questionnaire, Tinnitus History Questionnaire; Hospital Anxiety and Depression Scale; and the Tinnitus Functional Index, which is the primary outcome measure.

Data Analysis (Statistical Analysis Plan)

A Bayesian approach will be used to estimate the prevalence of somatosensory tinnitus in the VA population conditional on the phone screening data. The Bayesian prior probability distribution (i.e., “prior”) for this analysis is the meta-analysis based prediction derived from 4 published studies (Sanchez et al, 2002; Abel & Levine, 2004; Sanchez et al, 2007; Simmons et al, 2008). A sensitivity analysis will be conducted using a flat prior and a prior concentrated below 40% prevalence to evaluate the effects of the prior on the Bayesian posterior probability distribution.

We will evaluate the feasibility and tolerability of individualized physiotherapy performed in ~10 Veterans with somatosensory tinnitus. We will use the pilot data from questionnaires (e.g., TFI) and if available, 1 kHz loudness-matching results to document any reductions in tinnitus-related distress and perceived loudness following individualized physiotherapy. The change from baseline TFI score and 1 kHz loudness-match (in dB Sensation Level; dB SL) observed in this sample will provide the basis for sample size calculations in a subsequent large-scale Merit Review proposal.

Risks and Side Effects

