For the individualized physiotherapy, Veterans will be working one-on-one with the physical therapist who will provide both exercises and manual treatments (i.e., physiotherapy) to correct any deficits that are identified using standard of care clinical procedures. After a treatment session, there is a minimal risk that the subject may experience an increase in tinnitus, discomfort associated with the cervical spine, jaw, or thoracic spine. To minimize subjects experiencing discomfort, they will be educated on: 1) proper form of the exercises and expectations; 2) how to prevent worsening of symptoms; and 3) what to do if symptoms worsen.

Participant Safeguards

This study does not include vulnerable populations. Additional safeguards have been established to minimize risk of noise exposure.

Suicidality

It is not expected that potential subjects will be suicidal. In the unlikely event that an individual expresses suicidal ideation during the screening phone call or if he/she indicates that he/she is suicidal at any time during the study, a "warm transfer" procedure will be implemented to connect the individual with a person at the Suicide Hotline. All research staff will be informed of the warm transfer procedure and phone number for the National Crisis [contact] (Veterans press "1" and non-Veterans stay on the line).

Language is included in the informed consent form that if participants express thoughts about wanting to harm themselves or others, the Principal Investigator or study team member may call the National Crisis Hotline at [name] (Veterans press “1” and non-Veterans stay on the line) or walk them to the Emergency Department as appropriate.

Benefits

Tinnitus is the most prevalent service-connected disability for Veterans and currently has no “cure.” Hearing loss is the second most prevalence service-connected disability for Veterans. Subjects may or may not personally benefit from participating in this study. However, by serving as a subject, they will contribute new information expected to benefit patients in the future. Data generated from this research will help to assess the effectiveness of a new therapeutic approach to reduce tinnitus distress and partially, or completely, suppress the tinnitus perception.

Subjects will benefit by learning about tinnitus. In some cases, people who are bothered by their tinnitus are helped simply by receiving information and having their questions answered.

Protected Health Information

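### The TFI change meant to size the next trial has no comparator and only one specified pre-treatment score, so it could overstate the effect to plan on

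*Combined protocol and SAP*

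**What the plan says.** - **Treatment and design.** Under General Summary of Procedures, a subset of Veterans who screen positive "will be given the option to attend 3 in-person individualized physiotherapy sessions". No control, sham, waiting-list or randomised group is described anywhere.
- **Aim of the treated part.** Data Analysis (Statistical Analysis Plan): "We will evaluate the feasibility and tolerability of individualized physiotherapy performed in ~10 Veterans with somatosensory tinnitus". The questionnaires and any loudness matches are to document reductions after physiotherapy. No hypothesis test is planned.
- **Outcome and timing.** Screening/Baseline Tests lists "the Tinnitus Functional Index, which is the primary outcome measure". On later measurement it says only "In some cases, procedures will be repeated on later visits", without naming the procedures or the visits.
- **Use of the result.** The same SAP section says that the change from baseline in TFI and in the 1 kHz loudness match "observed in this sample will provide the basis for sample size calculations in a subsequent large-scale Merit Review proposal".
- **Benefits.** "Data generated from this research will help to assess the effectiveness of a new therapeutic approach". The next paragraph says that, in some cases, "people who are bothered by their tinnitus are helped simply by receiving information and having their questions answered".

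**The concern.** A before-after change with no comparator contains everything that happens to the score after the first measurement. Here that includes natural fluctuation, whatever the first visit does to the participant, information received, attention and expectation during the sessions, and any effect of the physiotherapy. The protocol itself names information as something that can help without treatment.

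For feasibility and tolerability this does no harm. It matters when the total change is carried forward as the planning effect. A controlled trial estimates the difference between arms, and improvement that would also occur in the control arm drops out of that difference. A trial sized on the total change would then have too few patients for the contrast it tests. The SAP contains no caution, adjustment or repeat baseline to guard against this.

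**Working it through.** The plan gives no alpha, power, effect size or SD, and no derivation of the figure of about 10. There is therefore no stated figure to reproduce.

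**1. How many pre-treatment visits?** Subject Compensation pays $30 per visit and $120 in total to those who attend all visits including physiotherapy: 120 / 30 = 4 visits. With three physiotherapy sessions, one visit remains before treatment. So the plan specifies one pre-treatment TFI, and session 1 is a separate return visit at which a second untreated score could be taken.

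**2. What if the raw change is used as a between-arm effect?** Assumptions, none from the documents: true effect d = 10 TFI points; net non-specific improvement b = 3 or 5 points; two-sided alpha 0.05; nominal power 80%; two equal arms; planning SD correct.

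Required sample size is proportional to 1/effect², so the fraction of the needed sample obtained is (d / (d + b))².

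- b = 3: (10/13)² = 0.59
- b = 5: (10/15)² = 0.44

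Actual power is Φ(2.80 × √fraction − 1.96), where 2.80 = 1.96 + 0.84.

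- b = 3: Φ(2.80 × 0.769 − 1.96) = Φ(0.195), about 58%
- b = 5: Φ(2.80 × 0.667 − 1.96) = Φ(−0.09), about 46%

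**3. The same question on a standardised scale.** Let f be the share of the total change that is non-specific. The required sample size grows by 1/(1 − f)². Take a total change of 0.5 SD (assumed):

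| f | Required n per arm | Ratio | Power if 63 per arm are enrolled |
|---|---|---|---|
| 0 | 63 | 1.00 | 80% |
| 25% | 112 | 1.78 | 56% |
| 50% | 252 | 4.00 | 29% |

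The values in step 2 correspond to f = 3/13 = 23% and f = 5/15 = 33%, so the two routes agree.

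**4. What can 10 patients estimate?** The 95% confidence interval for a mean change is ±2.262/√10 = ±0.72 SD of the change. The 95% interval for the SD runs from 0.69 to 1.83 times its estimate. Sample size scales with SD², so that uncertainty alone spans 0.69² = 0.48 to 1.83² = 3.35 times the calculated n.

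**5. How well would a repeat TFI at session 1 measure untreated drift?** Assume a TFI SD of 20 and a retest correlation r of 0.7 to 0.9. The SD of the untreated change is 20 × √(2(1 − r)).

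- r = 0.7: 15.5 points, 95% half-width 0.715 × 15.5 = 11.1
- r = 0.9: 8.9 points, 95% half-width 0.715 × 8.9 = 6.4

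So 10 patients give the drift only to within about ±6 to ±11 points. That would reveal a large shift but could not resolve one of 3 to 5 points.

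**The case against.** **This is a pilot, and an uncontrolled pilot is acceptable.** That stands for feasibility and tolerability, and no control arm is asked for here. It does not cover using the observed change to size the next study.

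**The protocol does not claim to test effectiveness.** A reader might infer from Benefits that it does. The documents do not support that: the sentence says only that the data will help in the assessment, and the SAP plans no such test. The remark that information can help does not contradict it either. The wording is a secondary matter.

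**The next trial need not be too small.** A reader might take underpowering as certain. It is not. The documents do not give the next trial's design or say that the mean change will be its between-arm difference. The direction is also open: Risks and Side Effects warns that tinnitus may become louder after auditory testing and that the musculoskeletal exam may aggravate symptoms. The exclusion of tinnitus management begun within the past month limits one source of drift.

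**Regression to the mean.** A reader might expect it to be large. Aim 2 sets no TFI threshold, so there is no selection on the score itself. Veterans who accept treatment may do so during a bad spell, but nothing in the documents gives a size, and none is claimed here.

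**A session 1 TFI may already be intended.** The sentence on repeated procedures does not exclude it. It does not specify it either.

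**A repeat TFI is a weak remedy.** Largely true. It is imprecise in 10 patients and leaves attention and expectation during treatment untouched. That is why the rule on how the change is used comes first in the fix.

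**Conclusion.** The point holds in a conditional form. The SAP makes an uncontrolled TFI change in about 10 Veterans the basis for sizing the next trial, with one specified pre-treatment score and no safeguard. That change cannot be divided into physiotherapy effect and non-specific change. A controlled trial could be too small if two things are true: the net non-specific change is an improvement, and the raw mean is used as the between-arm difference. The loss to about 58% or 46% power illustrates 3 or 5 assumed points of non-specific change on top of an assumed 10-point effect. It is not an estimate for this study. The imprecision of the pilot SD is a further reason for caution and does not depend on the direction of any bias. This is a cheap improvement of low severity.

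**What to change.** 1. **SAP, sizing sentence.** State that the raw before-after mean will not be used as the between-arm effect. Size the next trial on a justified meaningful difference, and use the pilot for the SD, with its confidence interval, and for retention.
2. **TFI time points.** Name them. Give the TFI again at the start of physiotherapy session 1, before any treatment, and name the final assessment. Record the interval from visit 1 to session 1, which is not stated now. Report the untreated change (visit 1 to session 1) separately from the change from session 1 to the end. Say in the SAP that this is only a partial remedy: it does not remove attention or expectation effects during treatment, and the drift estimate from 10 patients is imprecise.
3. **Benefits (secondary).** Reword the effectiveness sentence to refer to feasibility, tolerability and planning.

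**Cost.** A few minutes of questionnaire time for about 10 Veterans at a visit they already attend, and some wording. The reported treatment-period change will probably be smaller.
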